APPENDIX D: CLINICAL TECHNICAL PROCEDURES [REDACTED]

[REDACTED] Lens Fitting Characteristics

[REDACTED] Determination of Distance Spherocylindrical Refractions

[REDACTED] Biomicroscopy Scale

[REDACTED] Distance and Near Visual Acuity Evaluation

[REDACTED] Distance LogMAR Visual Acuity Measurement Procedure

[REDACTED] LENS FITTING CHARACTERISTICS

**[REDACTED] DETERMINATION OF DISTANCE SPHEROCYLINDRICAL
REFRACTIONS**

BIOMICROSCOPY SCALE

[REDACTED] DISTANCE AND NEAR VISUAL ACUITY EVALUATION

**[REDACTED] DISTANCE LOGMAR VISUAL ACUITY MEASUREMENT
PROCEDURE**

1. INTRODUCTION

1.1. Background

This document describes the data analysis specifications for study protocol CR-5830 titled "Evaluating the impact of JJVC senofilcon A-based contact lens with new UV-blocker on day and night driving performance" Version 3.0 Amendment 2.0 dated on September 14th, 2017. The test article is the JJVCI Investigational Contact Lens senofilcon A-based with new UV-blocker while the two controls are ACUVUE® OASYS® brand contact lens with HYDRACLEAR® Plus worn with spectacle frame without lenses (Control 1) and ACUVUE® OASYS® brand contact lenses with HYDRACLEAR® Plus worn with Transitions® XTRActiveTM- gray spectacles (Control 2)

This document will serve as the final guidance for all the statistical analysis for this study and will supersede section 14 in the protocol if there are any discrepancies (i.e. See Amendment History section)

The study aims to investigate the effect of senofilcon A contact lenses with new UV-blocker on vision and driving performance in both daytime and nighttime lighting under real world driving conditions. This will be achieved through field-based driving studies on a closed-road driving circuit at night and during the day. Quantitative methods will be used to assess vision and driving performance under a range of challenging conditions and appropriate masking, order of testing randomization and control conditions will be used.

1.2. Study Objectives

The objective of this study is to evaluate the effect of JJVC senofilcon A-based contact lens with new UV-blocker on vison and day and night driving performance under real world driving conditions. This study is intended to support the Pre-Market Notification, 510(k), submission of ACUVUE® (senofilcon A) Soft Contact Lens with New UV Blocker.

1.3. Study Design

This is a randomized, single-masked, crossover, dispensing study, with 4 visits. Comparisons between the JJVC investigational lens and the two controls will occur at visit 2 (vision testing) and visit 3 and 4 (driving performance). Approximately 28 subjects will be screened and enrolled to ensure that at least 24 subjects complete the study.

The study begins with an initial visit (Visit 1 - Day 0). If a subject is found to meet all eligibility criteria, he/she will be randomized to the Test lens and one of the Control lenses for an initial lens fitting evaluation using a 2x2 crossover design (Test/Control1, Test/Control2, Control1/Test, Control2/Test); otherwise, the subject will be deemed ineligible for this study.

After the fitting evaluation at Visit 1, non-discontinued subjects will be scheduled for three additional visits. Visit 2 will occur approximately 24 hours after the initial visit, visit 3 will occur approximately 24 hours after visit 2 and visit 4 will occur approximately 1 week after visit 3. At Visit 2, eligible subjects will be randomized and laboratory testing will be conducted on all test articles in a random order based on the randomization scheme. Subjective assessment of driving performance in both daytime and nighttime will be performed in a random order, based on the

randomization scheme, in two different visits at Visit 3 and Visit 4. Unscheduled follow-up visits may occur during the study. The planned duration of lens wear is for the experimental procedures only (between 1-3 hours during visits 2-4). Participants will not have access to test articles at study closure.

1.4. Statistical Hypotheses for Study Objectives

1.4.1. Primary Hypotheses

1. The Test lens will be non-inferior to the Control 1 lens with respect to overall night driving performance. A non-inferiority margin of -0.25 will be used.

1.4.2. Secondary Hypotheses

- 1. The Test lens will be non-inferior to the Control 1 lens with respect to binocular low luminance high contrast visual acuity. A non-inferiority margin of 0.1 LogMAR will be used.
- 2. The Test lens will be no different than the Control 1 lens with respect to low luminance low contrast threshold without glare.
- 3. The Test lens will be no different than the Control 1 lens with respect to the percentage of road signs correctly identified at night driving.
- 4. The Test lens will be no different than the Control 1 lens with respect to average distance to correctly identify a pre-determined road sign at night driving.
- 5. The Test lens will be no different than the Control 1 lens with respect to the percentage of hazards avoided at night driving.
- 6. The Test lens will be no different than the Control 1 with respect to average pedestrian recognition distance at night driving.

1.5. Sample Size Justification

The study is designed and powered to demonstrate non-inferiority of the Test lens relative to the Control 1 lens with respect to night driving performance score. Assuming no difference between the Test and Control 1 lens, the sample size was calculated using a non-inferiority margin of -0.25. The sample size of 24 subjects is consider sufficiently large to test for non-inferiority with a minimum power of 80% and a two-sided type I error of 0.05. The plan is to enroll 28 eligible subjects with a target completion of 24 subjects. During the enrollment period, the subject dropout rate will be closely monitored, if an unexpectedly high dropout rate is observed, the target enrollment will be increased accordingly to ensure a minimum of 24 subjects per group complete the study.

The non-inferiority margin and sample size calculations were based on available historical data from 6 published papers between 2009 and 2015 and from an investigator initiated study (IIS) sponsored by JJVC in 2016 that examined the effect of vision condition on driving performance. The Table below summarizes the studies considered in the meta-analysis.

I able 1: Summary of published papers considered in the meta-analysis Sample Age Driving Study Vision							
Year	Author	Paper Title	Sample Size	Age (Mean)	Driving Time	Study Group	Vision Condition
						Young	Corrected
						Middle-Age	Corrected
		Age and Visual				Older	Uncorrected
2002	Wood, JM	Impairment Decrease Driving Performance as	139	57.4	Day & Night	Older with ocular disease	Uncorrected
		Measured on a Closed-Circuit Road				older with moderate / severe ocular disease	Uncorrected
		Effects of Age				Young	Corrected
2005	Chaparro, A. et al.	Auditory and Visual Dual Tasks on Closed-Road Driving Performance	28	48.3	Day	Older	Uncorrected
2006	Wood,	Bilateral cataract	47	71.1	D	Normal vision	Corrected
2006	JM. et al.	surgery and driving performance	47	71.1	Day	Cataract	Uncorrected
	Wood, JM. et al.	Interaction between visual status, driver age and distracters on daytime driving performance	39	47.9		Normal vision	Corrected
2009					Day	Blur	Uncorrected
						Cataract	Uncorrected
	Wood, JM. et al.	Effects of Simulated Visual Impairment on Nighttime Driving Performance	20	27.5	Night	Normal vision	Corrected
2010						Refractive blur	Uncorrected
						Simulated cataract	Uncorrected
2012	Wood,	Useful Field of View Predicts Driving in	02	73.6	Day	Driving without visual distraction	Corrected
2012	JM. et al.	the Presence of Distracters	92	/3.0	Day	Driving with visual distraction	Uncorrected
						Spectacles w/ Blur 0.00D	Corrected
2014	Wood, JM. et al.	·	12	25.8	Day	Spectacles w/ Blur +0.50D	Uncorrected
2014				23.8	Night	Spectacles w/ Blur +1.00D	Uncorrected
						Spectacles w/ Blur +2.00D	Uncorrected
	Wood	Investigation of the impact of				ACUVUE OASYS	Uncorrected
2016	JM. et al.	uncorrected astigmatism on night driving performance*	10	24.4	Night	ACUVUE OASYS for Astigmatism	Corrected
2014 2016	JM. et al. Wood,	Day and Nighttime Driving Performance Investigation of the impact of uncorrected astigmatism on night driving performance [*]		25.8 24.4	Night	Spectacles w/ Blur +1.00D Spectacles w/ Blur +2.00D ACUVUE OASYS ACUVUE	Uncorre Uncorre Uncorre

 Table 1: Summary of published papers considered in the meta-analysis

*JJVC sponsored IIS study (not published)

After categorizing the vision condition of the study groups into a binary variable as corrected and uncorrected, a Bayesian random effect mate-regression model was conducted on the pooled data

to evaluate the overall effect of uncorrected vision on driving performance. The model can be written as

$$y_{ij}|\mu_{ij} = \mu_{ij} + e_{ij}; \text{ with } e_{ij} \sim N(0, S_{ij}^2)$$
$$\mu_{ij} = X_{ij}\beta + \delta_{ij}; \text{ with } e_{ij} \sim N(0, \sigma^2)$$

Here y_{ij} is the driving performance in vision condition group *i* in study *j*, X_{ij} is a vector of covariates from the *i*th vision condition group and *j*th study and β is the vector of regression coefficients. The term δ_{ij} is the random effect due to the between study variation while s_{ij}^2 represents the within study variation (known). The regression model included vision condition (corrected vs. uncorrected) and the covariates: driving time (day, night, day & night), average age and indicator variables of whether or not cone gap perception (not used in this study), course time and hazard avoidance were included in the calculation of the driving performance composite score.

We used independent vague normal N(0,1000) priors for the regression coefficients β , vague inverse-gamma with shape and scale parameters of 0.001 for the variance parameter σ^2 . The Metropolis sampler algorithm as implemented in the SAS MCMC Procedure (SAS/STAT 14.1, SAS Institute, 2015) was used to carry out parameter estimation. After a burn-in of 80,000 iterations, we run the algorithm for additional 500,000 iterations with a thinning factor of 100 to allow posterior chains of estimated parameters to converge. Convergence of the simulated chains was assessed using autocorrelation and sample trace plots.

The posterior mean difference in driving performance between corrected and uncorrected vision was estimated to be 0.579 with 95% credible interval (95% CrI) of (0.249, 0.917). The estimated variance was 0.0483 with 95% CrI of (0.0051, 0.1692).

With a sample size of 24 subjects, the estimated power for different scenarios of intra-class correlation (ICC) is shown in the table below:

Table 2. Statistical Fower by ICC						
Intra-class correlation	Between subject	Effect size	Power (%)			
(ICC)	variance σ^2					
.40	0.05	0.25	71			
.50	0.05	0.25	85			
.60	0.05	0.25	95			

 Table 2: Statistical Power by ICC

The sample size calculation was conducted using the PROC POWER Procedure (SAS/STAT 14.1, SAS Institute, 2015). The non-inferiority hypothesis testing problem of a 3x3 crossover design was formulated as a two-sample non-inferiority hypothesis testing (Peng Sun, 2010).

As discussed above, the estimated posterior mean difference in driving performance between corrected vision (treated) and uncorrected vision (untreated) was estimated to be 0.579 with 95% credible interval (95% CrI) of (0.249, 0.917). We therefore used the lower bound of the 95% credible interval as the non-inferiority margin (\sim -0.25). This represents a discount of 43% from the estimated difference between corrected vision and uncorrected vision.

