We used independent vague normal $N(0,1000)$ priors for the regression coefficients $\boldsymbol{\beta}$, vague inverse-gamma with shape and scale parameters of 0.001 for the variance parameter σ^2 . The Metropolis sampler algorithm as implemented in the SAS MCMC Procedure (SAS/STAT 14.1, SAS Institute, 2015) was used to carry out parameter estimation. After a burn-in of 80,000 iterations, we run the algorithm for additional 500,000 iterations with a thinning factor of 100 to allow posterior chains of estimated parameters to converge. Convergence of the simulated chains was assessed using autocorrelation and sample trace plots.

The posterior mean difference in driving performance between corrected and uncorrected vision was estimated to be 0.579 with 95% credible interval (95% CrI) of (0.249, 0.917). The estimated variance was 0.0483 with 95% CrI of (0.0051, 0.1692).

With a sample size of 24 subjects, the estimated power for different scenarios of intra-class correlation (ICC) is shown in the table below:

Table 5: Statistical Power by ICC

Intra-class correlation (ICC)	Between subject variance σ^2	Effect size	Power (%)
.40	0.05	0.25	71
.50	0.05	0.25	85
.60	0.05	0.25	95

The sample size calculation was conducted using the PROC POWER Procedure (SAS/STAT 14.1, SAS Institute, 2015). The non-inferiority hypothesis testing problem of a 3x3 crossover design was formulated as a two-sample non-inferiority hypothesis testing (Peng Sun, 2010).

As discussed above, the estimated posterior mean difference in driving performance between corrected vision (treated) and uncorrected vision (untreated) was estimated to be 0.579 with 95% credible interval (95% CrI) of (0.249, 0.917). We therefore used the lower bound of the 95% credible interval as the non-inferiority margin (\sim -0.25). This represents a discount of 43% from the estimated difference between corrected vision and uncorrected vision.

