5.2. Primary Analysis Methods

Overall driving performance score will be analyzed using a linear mixed model; sequence of lens wear, period, lens type, first order carry-over, driving time (day or night) and the 2-way interactions: lens*time, sequence*time, period*time and carry*time will be included in the model as fixed effects. Age will be included as fixed covariate when appropriate. An appropriate covariance structure will be selected to model the correlation between measurements across periods within the same subject and driving time. Covariance structures that will be considered include:

- Compound Symmetry (CS)
- Heterogeneous Compound Symmetry (CSH)
- Unstructured (UN)
- Ante-dependence (ANTE(1))

For ANTE(1) structure, subject and driving time nested within subject will be included in the model as random effects. For the remaining structures only subject will be included as random effect. The covariance structure that returns the lowest Akaike Information Criteria Corrected (AICC) will be selected as the structure that best fit the data¹². Heterogeneous residuals covariance structures (R-side) across driving time will be considered when appropriate. The log-likelihood ratio test will be used to test for the homogeneity between the residual covariance structures. The Kenward and Roger method will be used for the denominator degree of freedom. Non-significant interactions at the 15% significance level will be excluded from the model. The interaction between lens type and driving time will be forced into the final model.

Comparisons between Test and Control 1 will be conducted overall across driving time and within each level of driving time. Results from the final selected model will be reported as least-square mean (LSM) differences with 95% confidence intervals.

The null and alternative hypotheses for non-inferiority of Test lens relative to Control 1 are as follows:

$$H_0: \mu_T - \mu_C \le -0.25 H_A: \mu_T - \mu_C > -0.25,$$

where μ_T and μ_C are the means of night driving performance score for Test and Control 1, respectively. Non-inferiority of the Test relative to Control 1 will be concluded if the lower limit of the 95% confidence interval of the LSM difference between Test and Control 1, at night driving time, is greater than - 0.25.

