APPENDIX A SAS SYNTAX CODE

Primary Endpoint:

Overall driving performance scores

PROC GLIMMIX DATA = ads plots=studentpanel; CLASS driveseq asper trta carry1a parcat5 subjid sexn; MODEL aval= age sexn driveseq|parcat5 asper|parcat5 trta|parcat5 carry1a|parcat5/ DDFM=KR2 S; RANDOM INTERCEPT / SUBJECT=subjid; **RANDOM INTERCEPT / SUBJECT = parcat5(subjid);** *only included if ANTE(1) is used; RANDOM asper / RESIDUAL SUBJECT=parcat5(subjid) TYPE=covariance matrix group=parcat5; **Remove GROUP = time from the statement above if the test for homogeneity is rejected at 5% significance level; COVTEST "Common Varaince" Homogeneity; **test for homogeneity used along with GROUP = time; LSMEANS trta*parcat5 /slicediff = parcat5 CL ; **Primary analysis; ESTIMATE "Night: Test vs Control1" trta -1 0 1 trta*parcat5 0 -1 0 0 0 1 / CL; **Other Analysis; ESTIMATE "Day: Test vs Controll" trta -1 0 1 trta*parcat5 -1 0 0 0 1 0, "Day: Test vs Control2" trta 0 -1 1 trta*parcat5 0 0 -1 0 1 0, "Night: Test vs Control2" trta 0 -1 1 trta*parcat5 0 0 0 -1 0 1 / ADJUST= bonferroni CL;

RUN;

Where ads: Analysis data set subjid: subject identification aval: overall driving performance score sexn: Gender driveseq: Lens wear sequence (6 levels) asper: Study Period (3 levels) trta: Study lens type (Test, Control1, Control2) parcat5: Driving time (day or night) carry1a: First order carryover effect covariance_matrix: CS, CSH, UN and ANTE(1). The covariance structure that returns the lowest AICC will be selected as the structure that best fit the data.

Secondary Endpoints:

Binocular distance visual acuity (LogMAR)

PROC GLIMMIX DATA = ads plots=studentpanel; CLASS TSEQPG2 aperiod trta carry1a subjid sexn ; MODEL aval= age sexn tseqpg2 aperiod trta carry1a / DDFM=KR2 ; RANDOM INTERCEPT / SUBJECT=subjid; *only included if ANTE(1) is used; RANDOM aperiod / RESIDUAL SUBJECT=subjid TYPE=covariance_matrix ; LSMEANS trta / CL; ESTIMATE "Test vs Control1" trta -1 0 1, *secondary analysis; "Test vs Control2" trta 0 -1 1 / CL; *other analysis; RUN; Where ads: Analysis dataset subjid: subject identification sexn: Gender tseqpg2: Lens wear sequence (6 levels) aperiod: Study Period (3 levels) trta: Study lens type (Test, Control1, Control2) carry1a: First order carryover effect covariance_matrix: CS, CSH, UN and ANTE(1). The covariance structure that returns the lowest AICC will be selected as the structure that best fit the data.

Low Luminance contrast threshold

PROC GLIMMIX DATA= ads;

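### The power table uses a between-study variance and does not match the planned test, so the claim of at least 80% power is unsupported, though not shown to be false

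*SAP*

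**What the plan says.** SAP 1.5, like Protocol 14.2, bases N on non-inferiority of Test to Control 1 for the night driving score. The true difference is taken as 0 and the margin as -0.25. Twenty-four completers are said to be enough "with a minimum power of 80% and a two-sided type I error of 0.05".

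The inputs come from a meta-regression of group-level driving scores. Its random term "is the random effect due to the between study variation", with variance σ². One variance is reported: "The estimated variance was 0.0483 with 95% CrI of (0.0051, 0.1692" being the credible interval. The power table (Protocol Table 5, SAP Table 2) then has a column headed "Between subject variance" σ², equal to 0.05 in every row, with powers of 71, 85 and 95% at ICC 0.40, 0.50 and 0.60. The crossover problem "was formulated as a two-sample non-inferiority hypothesis testing" and run in PROC POWER; the call is not shown.

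The test itself is set in SAP 5.2. Non-inferiority is concluded if the "lower limit of the 95% confidence interval of the LSM difference between Test and Control 1, at night driving time" lies above -0.25. The mixed model contains first-order carry-over and its interaction with driving time. In SAP Appendix A the fixed effects end "driveseq|parcat5 asper|parcat5 trta|parcat5 carry1a|parcat5/ DDFM=KR2 S". Interactions can drop out: "Non-significant interactions at the 15% significance level will be excluded from the model".

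**The concern.** Four things do not fit together.

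- **Variance.** The spread of adjusted group means across studies does not measure how much one driver's score varies between lenses or between drivers. Power for this trial depends on the within-subject variance at night, which neither document gives.
- **Minimum power.** The table's first row is 71%, below the 80% stated as a minimum, and nothing in the text rules out an ICC of 0.40.
- **Alpha and layout.** A 95% confidence limit is a one-sided 2.5% test. Every subject wears all lenses, so the comparison is within subject and not between two independent groups.
- **The 43%.** The margin is described as a 43% discount on the estimated effect, but 43% is the part kept.

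This table is the only quantitative support for N. If the lower limit fell below -0.25, the sponsor could not tell from the plan whether the lens or the sample size was the cause.

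**Working it through.** **Inputs.** True difference 0, margin 0.25 and N = 24 (SAP 1.5). Variance 0.0483, credible interval 0.0051 to 0.1692 (SAP 1.5), or the table's 0.05. ICC 0.40, 0.50, 0.60 (power table). One-sided 2.5% (decision rule, SAP 5.2). My assumptions are ICC = σ_b²/(σ_b² + σ_w²), compound symmetry, and 24 completers balanced over the six sequences.

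**Step 1: within-subject variance implied by the table.** σ_w² = σ_b²(1 − ICC)/ICC. With 0.0483 this is 0.0483 × 0.6/0.4 = 0.072, then 0.048 and 0.032. With 0.05 it is 0.075, 0.050 and 0.033.

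**Step 2: reproduce the table.** Two-sample t-test, 12 per group, variance of the difference 2σ_w²/12, 22 degrees of freedom, noncentrality 0.25/√(2σ_w²/12).

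| Variance | One-sided alpha | ICC 0.40 | 0.50 | 0.60 |
|---|---|---|---|---|
| 0.0483 | 5% | 71.2 | 85.4 | 95.2 |
| 0.05 | 5% | 69.9 | 84.3 | 94.6 |
| 0.0483 | 2.5% | 58.5 | 75.9 | 90.3 |
| 0.05 | 2.5% | 57.1 | 74.5 | 89.3 |

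The first row matches the printed 71/85/95. With the printed 0.05, the same contrast variance and 42 degrees of freedom, one-sided 5% gives 71.05/85.30/95.10, which also rounds to the table. No variant tried at one-sided 2.5% matches. With 0.0483, 24 per group gives 88.3/97.1/99.7 and paired n = 24 gives 86.9/96.5/99.6.

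**Step 3: the planned contrast.** Inverting the design matrix of the six-sequence design with 24 subjects gives these variances for Test minus Control 1 at night:

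- 2σ_w²/24 without carry-over (44 df)
- 2.25σ_w²/24 with one carry-over effect shared by day and night (44 df used)
- 2.5σ_w²/24 with carry-over by driving time (42 df)

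The removal rule in SAP 5.2 names interactions only, so the carry-over main effect stays. The last two lines are therefore the planned cases and the first is a reference. Power (%) at one-sided 2.5%, by ICC 0.40/0.50/0.60:

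| Variance | No carry-over | Carry-over pooled | Carry-over by time |
|---|---|---|---|
| 0.0483 | 88.2/97.1/99.7 | 84.3/95.3/99.4 | 80.3/93.1/98.8 |
| 0.05 | 87.1/96.6/99.6 | 83.0/94.6/99.2 | 78.9/92.3/98.6 |
| 0.1692 | 39.0/54.0/71.3 | 35.4/49.3/66.2 | 32.4/45.2/61.5 |

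At the lower credible limit, 0.0051, power with carry-over by time is about 100% at all three ICCs.

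**Step 4: break-even.** For 80% power σ_w² may be at most 0.091, 0.081 or 0.073 in the three models. The table's ICC 0.40 row has 0.072 (0.075 with 0.05), which is at the limit of the fullest model. The lowest ICC giving 80% is 0.35, 0.37 or 0.40 with variance 0.0483, and 0.65, 0.68 or 0.70 with 0.1692. The last three lie outside the table.

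**Step 5: the discount.** 0.249/0.579 = 0.430 is the share of the estimate kept as the margin. The reduction is 1 − 0.430 = 0.570, or 57%.

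**The case against.** The strongest reply is that a correct calculation on the plan's own inputs helps the sponsor. At one-sided 2.5% the crossover gives about 79 to 88% at ICC 0.40 and over 92% at the other two. The only cell below 80% is 78.9%, in the fullest model with 0.05, and that model applies only if the carry-over by time interaction survives the 15% screen. This stands, and it is why the finding is not one of underpowering. Those figures still carry the unsupported variance.

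A second reply is that no sentence says the table's 0.05 is the 0.0483, and that 12 per group is my reconstruction; the text itself speaks of 24 per group. That is also true. The exact match in Step 2 is not unique, since 0.05 with 42 degrees of freedom fits as well. But the symbol is the same, the value is 0.0483 rounded, no other variance is reported, and the section says the calculation was based on that meta-analysis. Both matches need one-sided 5%, so the second one supports the alpha point.

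A third reply is that 0.1692 is no more a subject-level variance than 0.0483. Agreed. The last row of the crossover table in Step 3 shows only how far the claim moves within the plan's stated uncertainty. It does not estimate this trial's power.

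**Conclusion.** The concern holds. The 80% minimum is contradicted by the table's 71% row, and the table rests on a variance that does not describe subjects. It also fits a one-sided 5% two-group test and not the planned one-sided 2.5% within-subject test. That last point is the likeliest explanation of the printed figures, not proof, because the software call is missing.

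The looser alpha overstates power: in the same layout with 0.0483 the planned alpha lowers 71/85/95 to 59/76/90. The two-group layout understates it: the crossover raises those figures to 84/95/99 with pooled carry-over or 80/93/99 with carry-over by time. On its own variance the printed table is therefore somewhat pessimistic. Whether 24 completers are enough turns on whether the night within-subject variance is below about 0.073 to 0.081 in the planned models, and the documents do not say. This rests on compound symmetry, balance over sequences and, for the pooled case, equal day and night variances. The SAP allows other covariance structures. The fault should be fixed, but it does not touch N, the margin or the decision rule.

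**What to change.** In SAP 1.5 and Protocol 14.2:

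1. Recompute the power table at one-sided 0.025 with the crossover contrast: 2.25σ_w²/24 if carry-over is kept and its interaction with time dropped, 2.5σ_w²/24 if the interaction is kept, and 2σ_w²/24 as a reference. State the software call, alpha and n.
2. Take σ_w² and the ICC from subject-level composite scores and name the source. Show a sensitivity range, because the available night data are small (the 2016 night study has 10 subjects).
3. State the range of σ_w² or ICC over which 80% holds, and drop the word minimum outside it.
4. Correct the variance label in the table, and change the 43% discount to 57%.

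The cost is one rerun of the calculation and edits to one paragraph and one table in each document. The stated power may go up or down.
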